#### 11.4.1.2. Definition of Serious Adverse Event

The ICH topic E2A on Clinical Safety Data Management, Definitions and Standards for Expedited Reporting defines an SAE as any untoward medical occurrence that at any dose:

- Results in death
- Is life threatening  
NOTE: The term "life threatening" in the definition of "serious" refers to an event in which the patient was at risk of death at the time of the event; it does not refer to an event which hypothetically might have caused death if it were more severe.
- Requires inpatient hospitalization or prolongation of existing hospitalization
- Results in persistent or significant disability/incapacity
- Is a congenital anomaly/birth defect

Medical and scientific judgment should be exercised in deciding whether expedited reporting (see Section 11.4.1.10) is appropriate in other situations, such as important medical events that may not be immediately life threatening or result in death or hospitalization but may jeopardize the patient or may require intervention to prevent one of the other outcomes listed in the definition above. These should also usually be considered serious. Examples of such events are intensive treatment in an emergency room or at home for allergic bronchospasm; blood dyscrasias or convulsions that do not result in hospitalization; or development of drug dependency or drug abuse.

To ensure there is no confusion or misunderstanding of the difference between the terms “serious” and “severe”, the following note of clarification is provided:

The term “severe” is often used to describe the intensity (severity) of a specific event (as in mild, moderate, or severe myocardial infarction); the event itself, however, may be of relatively minor medical significance (such as severe headache). This is not the same as “serious,” which is based on patient/event outcome or action criteria usually associated with events that pose a threat to a patient’s life or functioning. Seriousness (not severity) serves as a guide for defining regulatory reporting obligations.

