#### 11.4.1.6. Assessment of the Outcome of Adverse Events

The action taken for study drugs (eg, dose increased, dose not changed, dose reduced, dose interrupted, drug withdrawn, not applicable, unknown) will be recorded on the eCRF.

Other actions (eg, none, concomitant medication given, new or prolonged hospitalization, procedural surgery) will also be recorded on the eCRF.

The outcome will be assessed according to the following:

- Fatal
- Not recovered/not resolved
- Recovered/resolved with sequelae
- Recovering/resolving
- Recovered/resolved
- Unknown

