#### 11.4.1.8. Documentation of Adverse Events and Serious Adverse Events

All AEs will be documented in the appropriate section of the eCRF. The CTCAE, Version 4.03 grading scale referenced in [Appendix 1](#) is provided to assist in categorizing and grading AEs. All SAEs (see Section [11.4.1.2](#)) will be additionally documented on the SAE report form. For AEs occurring while the patient is in the clinic setting, ie, before, during, or after study drug administration, the start time and stop time of the AE should be recorded in the source document.

The following will be recorded for each AE in the eCRF:

- A description of the AE in medical terms, not as reported by the patient. Whenever possible, a diagnosis should be given when signs and symptoms are due to common etiology (eg, cough, runny nose, sneezing, sore throat, and head congestion should be reported as “upper respiratory infection”).

- Date of onset (start date)
- Date of recovery (stop date)
- Grade as assessed by the investigator according to the definitions in the AE Grading Scale. If the AE is not specifically listed in [Appendix 1](#), use the following grades:
  - Grade 1 mild
  - Grade 2 moderate
  - Grade 3 severe
  - Grade 4 life-threatening or disabling
  - Grade 5 death

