#### 11.4.1.12. Regulatory Aspects of Adverse Event Reporting

Unexpected serious adverse reactions are subject to expedited reporting to the Food and Drug Administration (FDA) and European National Competent Authorities, the Medicine Evaluation Board, and the Competent Authorities in other Member States, if applicable, in an expedited time frame in compliance with current legislation. The sponsor or its representative will report all unexpected SAEs to the Competent Authority, the Medicine Evaluation Board, and the Competent Authorities in other Member States, as applicable in an expedited time frame.

All SAEs must be entered into the SAE form and sent to the medical monitor /drug safety team within 24 hours of first knowledge of the event by the study personnel.

The investigator is encouraged to discuss with the medical monitor any adverse experiences for which the issue of reportability is unclear or questioned.

It is important that the investigator provide his/her assessment of relationship to study drug at the time of the initial report. The following information must be reported on the eCRF SAE report form:

- Protocol number
- Site and/or investigator number
- Patient number
- Demographic data
- Brief description of the event
- Onset date and time
- Resolution date and time, if the event has resolved
- Current status, if event has not yet resolved
- Any concomitant treatment and medication
- Investigator's assessment of whether the SAE was related to investigative product or not
- Outcome of the event if available

The medical monitor or member of the safety team will contact the site for clarification of data entered in the eCRF, or to obtain missing information. In the event of questions regarding SAE reporting, the site may contact the medical monitor or a member of the safety team.

G1 Therapeutics, or their designee, and their collaborators are responsible for submitting reports of AEs associated with the use of the study drug that are both serious and unexpected to the FDA and European National Competent Authorities, the Medicine Evaluation Board,

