5.1.3. Supportive Secondary Endpoints

5.1.3.1. Total Number of Major Adverse Hematologic Events (MAHE)

As a composite measure of trilaciclib effect, MAHE is based on a combination of individual components specified in [Table 4](#), which also include details about the derivation or data source for each component. For each component of composite MAHE, its number of events is derived as the number of episodes with a unique start date during the induction treatment period between the date of randomization and the end of the last induction cycle (i.e. last cycle of placebo or trilaciclib plus E/P/A). A patient with absence of an episode will be assigned a value of 0 to the number of events for this component. Then, the total number of MAHE during the induction treatment period is obtained as the summation over all components of composite MAHE during the induction treatment period.

Table 4 Component of MAHE and the Suggested Data Source/Derivation Algorithm

Seq #	Component of MAHE	Details
1	All-cause hospitalizations	Each hospitalization is captured in the AE data of the electronic database. Each recorded Preferred Term (PT) with a unique start date will be counted as an event, e.g. if a patient is hospitalized and several preferred terms are attributed to that hospitalization with the same start date, then the event is only counted once. The event terms are coded using the Medical Dictionary for Regulatory Activities (MedDRA) Version 20.1.
2	All-cause dose reductions	Detailed in Section 5.1.2.3
3	Febrile neutropenia	Detailed in Section 5.1.3.10
4	Prolonged severe (Grade 4) neutropenia (duration > 5 days)	Detailed in Section 5.1.1.2.1 . Each cycle with a duration greater than 5 days will be counted as an event with the date of the first grade 4 lab value defined as the start date for the time-to-first event analysis.

Seq #	Component of MAHE	Details
5	RBC transfusion on/after 5 weeks	Detailed in Section 5.1.2.1

A patient with absence of any episode of MAHE will be assigned a value of 0 for the total number of MAHE. Additionally, a sensitivity analysis will be done for dose reductions and RBC transfusions on/after 5 weeks, that excludes patients who do not start a second cycle of treatment.

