5.2.2. Adverse Events (AEs)

All AEs will be coded from verbatim text to PTs and grouped by SOC using the MedDRA Version 20.1. AEs will be collected from the time of signature of informed consent throughout the treatment period and up to 30 days after the last dose of study treatment. SAEs and AESI will be collected through 90 days after the last dose of study drug. AEs are graded by investigator according to CTCAE, Version 4.03.

For the induction treatment period, TEAE analyses will include all AE’s that started on or after the first dose of study drugs and up to the date of first dose of atezolizumab in the maintenance period. If the subject did not enter the maintenance period, then AEs up to the first dose of the last cycle in the induction period + 36 days (inclusive) will be considered TEAE.

For the maintenance treatment period, TEAE analyses will include all AE's that started on or after the first dose of atezolizumab in the maintenance period through the last dose of the maintenance period + 30 days.

For TEAEs that are designated as SAEs or AESIs, data will be summarized through the last dose of atezolizumab + 90 days.

TEAEs will be summarized overall and by the period in which they occur.

Other AE variables include drug-related AEs, AEs leading to study drug discontinuation or study withdrawal, AEs leading to death, SAEs, and atezolizumab AESIs.

AEs with onset/end dates that are partially/completely missing will be imputed as follows:

(i) For onset date:

- If only the day part of the AE onset date is missing and occurs in the same month and year as the first dose date of study drug, the date of first dose of study drug will be used as the onset date of the AE. Otherwise, the first day of the month will be used to complete the onset date of the AE;
- If the day and month parts of the AE onset date are missing and occur in the same year as the first dose of study drug, the date of the first dose of study drug will be used as the onset date of the AE. Otherwise, January 1st will be used to complete the onset date of the AE;
- If the AE onset date is completely missing, the date of the first dose of study drug will be used as the onset date of the AE.

(ii) For end date:

- If only the day part of the AE end date is missing, the last day of the month will be used to complete the end date of the AE;
- If the day and month parts of the AE end date are missing, December 31st will be used to complete the end date of the AE;

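### SAP Table 4 counts dated preferred terms, not inpatient stays, so one hospitalization can be counted more than once in the hospitalization component and in total MAHE

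*SAP*

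**What the plan says.** SAP Section 5.1.3.1 sets a general rule for every MAHE component: "its number of events is derived as the number of episodes with a unique start date during the induction treatment period". It does not define an episode. Total MAHE is the sum over the five components.

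For hospitalizations, Table 4 takes the data from AE records and gives the unit: "Each recorded Preferred Term (PT) with a unique start date will be counted as an event". It then illustrates: if "several preferred terms are attributed to that hospitalization with the same start date, then the event is only counted once". Nothing is said about terms of one hospitalization that start on different dates. Section 5.1.3.1.1, on all-cause hospitalizations, only refers back to 5.1.3.1.

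The protocol shows what those records hold:
- Section 11.4.1.8 records the AE's date of onset as its start date. The SAE report items in Section 11.4.1.12 include "Onset date and time". Neither list names an admission or discharge date.
- Section 11.4.1.2 has the seriousness criterion "Requires inpatient hospitalization or prolongation of existing hospitalization".
- Section 11.4.1.6 has, among the actions recorded for an AE, "new or prolonged hospitalization".

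SAP Section 6.2.7.2.1 analyzes total MAHE with a negative binomial model (two-sided p-value, adjusted rate ratio, event rate per week) and summarizes the component counts similarly. SAP Table 3 lists MAHE and all-cause hospitalizations among the prospectively defined analyses.

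**The concern.** A result labelled as a number of hospitalizations should be a number of stays. Table 4 counts something else: distinct onset dates of AE terms linked to hospitalization. A patient admitted with one event who develops a second a few days later, during the same stay, can contribute two hospitalizations. If an AE that only prolongs a stay carries the same flag, it can add another.

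Two things are at stake. The first is the level: the component count, total MAHE and the weekly event rates may be higher than the number of stays justifies. The second is the comparison: if dated terms per stay differ between arms, the rate ratio for hospitalizations, and to a lesser degree for total MAHE, moves away from the ratio of stays.

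**Working it through.** The documents state no hospitalization rate, MAHE rate or number of terms per stay, so there is no plan figure to reproduce. The check is a reading of the rule followed by arithmetic on assumed values.

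**1. The rule applied to assumed records for one patient.** Stay A has three terms with onset on Days 10, 11 and 13. Stay B has two terms, both with onset on Day 40.
- Table 4 as written: Days 10, 11, 13 and 40 give 4 events. The same-date example merges only the two Day 40 terms.
- Count of stays: 2.

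**2. Level.** Let m be the mean number of dated terms counted per stay. The share of counted hospitalizations that are repeats is (m − 1)/m. At an assumed m = 1.2 this is 0.2/1.2 = 17%. For stays with k terms, where each extra term has probability q of a new onset date, m = 1 + (k − 1)q. With k = 2 and q = 0.25, m = 1.25; with k = 3 and q = 0.75, m = 2.5. Stays with a single term pull the average towards 1.

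**3. Hospitalization rate ratio (trilaciclib vs placebo).** Ratio of counts = ratio of stays × (mT/mP). With equal true admission rates the first factor is 1:
- 1.2 vs 1.2: 1.2/1.2 = 1.00
- 1.1 vs 1.3: 1.1/1.3 = 0.85; reversed, 1.3/1.1 = 1.18
- 1.1 vs 1.5: 1.1/1.5 = 0.73; reversed, 1.5/1.1 = 1.36

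**4. Total MAHE.** With h admissions and c other component events per patient, equal in both arms, the ratio is (h·mT + c)/(h·mP + c). Assumed ranges are h = 0.2 to 0.5 and c = 0.5 to 1.5. The extremes are:

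| mT vs mP | h = 0.5, c = 0.5 | h = 0.2, c = 1.5 | Reversed |
|---|---|---|---|
| 1.1 vs 1.3 | 1.05/1.15 = 0.91 | 1.72/1.76 = 0.98 | 1.10 and 1.02 |
| 1.1 vs 1.5 | 1.05/1.25 = 0.84 | 1.72/1.80 = 0.96 | 1.19 and 1.05 |

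**5. Where the count does not reach.** Time to first MAHE, overall and per component (SAP Sections 5.1.3.1 and 6.2.7.2.1), uses only the first event, so repeats within a stay do not change it. The MAHE subgroup summaries in SAP Section 6.2.9 receive the count but are descriptive.

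**The case against.** The strongest reply is that Table 4 does not forbid a wider merge. The same-date case is only an example, its point is that one hospitalization counts once, and the table's title calls the algorithm suggested. Nor is there a sharp conflict with the general rule, since *episode* is undefined and both sentences turn on a unique start date. This stands in part: a programmer could read the intention as one event per stay. But no other algorithm is given, and nothing merges terms by admission. If the start date meant the admission date, terms of one stay would always share it and the condition in the example would add nothing.

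A second reply is that repeats may be rare. Protocol Section 11.4.1.8 asks for a diagnosis, where possible, when signs and symptoms have a common cause. Section 11.4.1.1 places laboratory abnormalities linked to a clinical event under comments, not as separate AEs. Both limit terms per stay without removing the problem. The eCRF is not supplied and the SAP does not say which field identifies a hospitalization, so whether prolongation-only AEs enter the count is also open.

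A reader might infer that the treatment comparison is biased or its type I error inflated. The documents do not support that. The ratio moves only if terms per stay differ by arm, and no data on this are given. The trial is double-blind (Protocol Section 8.5), and the 1.1 versus 1.5 case assumes a five-fold difference in extra terms per stay (0.5/0.1). Protocol Section 4.3.1 reports fewer high-grade hematologic events with trilaciclib in Study G1T28-02. That makes a difference conceivable but says nothing about terms per stay. If one arm did have more in-hospital complications, part of the difference would be real AE burden, though not more hospitalizations.

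**Conclusion.** The concern holds as a defect in a stated counting rule. Read as written, Table 4 can return more hospitalizations than stays, and the excess passes into total MAHE by summation. Its frequency and direction cannot be known from the documents. Equal over-counting leaves the rate ratio about unchanged; the values in the working (0.73 to 1.36 for hospitalizations, 0.84 to 1.19 for total MAHE) only illustrate assumed between-arm differences with equal true admission rates.

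A reader might also infer that a confirmatory claim is at risk. Under this SAP it is not. MAHE is supportive (Protocol Section 13.5.4, Region 2; SAP Section 5.1.3.1), and neither MAHE nor hospitalizations is among the five hypotheses in SAP Section 6.2.7.1.4. Protocol Section 13.5.3.1 does place both in the Region 1 testing procedure, but the Region 1 SAP is not among the documents, so nothing can be said about how it counts stays. The point is worth correcting because the label and the count may disagree and the correction is cheap.

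**What to change.** - In Table 4, define one hospitalization per inpatient stay. Terms attributed to the same stay count once whatever their onset dates, and an AE that only prolongs a stay adds no event. Align the episode wording in Section 5.1.3.1 with this.
- Use admission and discharge dates if they are collected.
- If they are not, have patients with several hospitalization-flagged terms assigned to stays by blinded review before database lock. SAP Section 5.1.3.2.4 already provides a pre-lock review for best overall response cases that its table does not cover.
- Use overlap of AE dates only as a screen for that review. AEs are followed until they resolve (Protocol Section 11.4.1.11), so one that outlasts discharge can overlap a later stay and merge two admissions, while non-overlapping AEs can split one stay.

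The cost is SAP wording, a change to the derivation code and a small review. Hospitalization and MAHE counts may be lower as a result.

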Time to first occurrence of a MAHE will be used as a sensitivity analysis in support of the total number of MAHE. It is defined as the first time to observe an event among all the components, starting from the date of randomization. Therefore, for a patient with presence of MAHE, time (months) to first occurrence of a MAHE will be the minimum among the 5 potentially derived durations (i.e. calculated as (date of first occurrence of a MAHE component event – date of randomization + 1)/30). A patient without any MAHE will be censored at the end of the last cycle (i.e. last cycle of placebo or trilaciclib), death, end of study, or date of last contact, whichever is earlier.

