The tipping-point analysis assumes all possible combinations of numbers of Yes and No for the missing responses (defined as patients without an event who have less than 4 induction cycles) in the trilaciclib and placebo groups. For example, let n_t be the number of randomized trilaciclib patients with missing response and n_c be the number of randomized placebo patients with missing responses. For the trilaciclib patients with missing values, there are $n_t + 1$ possible assumptions for number of No (i.e. 0, 1, 2, ..., to n_t); for the placebo patients with missing values, there are $n_c + 1$ possible assumptions for number of No. Therefore, there are total of $(n_t + 1) \times (n_c + 1)$ possible combination of assumptions for number of No and Yes for the trilaciclib and placebo patients with missing responses. The un-stratified exact CMH method will be performed on the available responses with each of these $(n_t + 1) \times (n_c + 1)$ assumptions and will be summarized. A figure will be presented with points representing each possible combination where the significant p-value 'tips' to greater than a one-sided 0.025, which would represent a change in the study conclusions. Clinical justification will be provided to evaluate whether the assumption is plausible.

A waterfall plot showing the number of induction cycles with SVN will be presented.

DSN for each induction cycle will be presented using descriptive statistics. The primary analysis on DSN defined by Strategy 1 (refer to [Section 6.2.7.1.1](#)) will be repeated on DSN defined by Strategy 3 (refer to [Section 5.1.1.2.3](#)).

Each of the analyses will be repeated using two additional distinct data sets to evaluate the confounding effect of GCSF administration: inclusion of only those patients or cycles who had concurrent GCSF administration; and inclusion of only those patients or cycles who did NOT have concurrent GCSF administration. The "with" and "without" GCSF analyses are subsets of the total number of patients or cycles.

DSN, Strategy 2 (refer to [Section 5.1.1.2.2](#)) endpoint will be summarized using Kaplan-Meier method, and the descriptive statistics of median, 25% and 75% percentiles along with their 95% CIs will be calculated. Additionally, DSN for each cycle will be presented using descriptive statistics.

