In addition to the summary from Kaplan-Meier method, the two-sided p-value will be obtained from the stratified Kaplan-Meier method to account for the stratification factors. The hazard ratio (HR) between the two treatments (trilaciclib vs placebo), together with its 95% CIs will be calculated from a Cox proportional hazard model in which treatment and the stratification factors will be included as fixed effects.

For the time (days) to first occurrence of a MAHE event, a graphical display of cumulative incidence will be presented.

The primary and key secondary efficacy endpoints are based on the ITT analysis set, and the analysis will be repeated for the mITT analysis set and PP analysis set.

For RBC transfusions, subsets of subjects with baseline HGB <9 g/L and ≥ 9 g/L will be provided, as well as a summary of the number of units transfused.

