6.2.7.2 Supportive Secondary Efficacy Analyses

6.2.7.2.1 Analyses of Total Number of MAHE

The total number of MAHE in [Section 5.1.3.1](#) will be analyzed to compare trilaciclib and placebo using a negative binomial regression model to account for the potential over-dispersion. The model includes the stratification factors of ECOG (0 or 1 vs. 2) and brain metastases (Yes vs. No), and treatment as a fixed effect. The logarithm transformation of duration of induction treatment period divided by 7 (i.e. week) will be included as an offset variable in the modeling. The two-sided p-value, aRR (trilaciclib vs placebo) and its 95% CIs will be presented.

The total number of MAHE will be summarized descriptively, along with the weeks of induction treatment duration, and the event rate per week (calculated as the total number of events/duration of induction treatment period divided by 7 [i.e. week]). The cumulative incidence of events during the induction treatment period will be summarized and presented graphically in three-week intervals.

The total number of individual MAHE components (specified in [Table 4](#)) will be summarized similarly, except that DSN > 5 days will be summarized cumulatively by cycle instead of three week intervals, and the offset will be the logarithm transformation of number of induction cycles divided instead of duration of induction treatment period.

Time-to-first MAHE endpoints (overall and individually) in [Section 5.1.3.1](#) will be summarized similar to DSN, Strategy 2 as described in [Section 6.2.7.1.5](#). A graphical display of cumulative incidence will also be presented.

An event chart of the induction treatment period will also be included, with horizontal bars for each subject's cycle length and time on the x-axis, with points plotted for each of the MAHE components.

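### Time to first MAHE censors death, so the planned Kaplan-Meier summary and cumulative-incidence display overstate incidence (minor)

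*SAP*

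**What the plan says.** The role of the analysis is set in SAP 5.1.3.1: "Time to first occurrence of a MAHE will be used as a sensitivity analysis in support of the total number of MAHE". The clock runs from randomization to the earliest event among the five components. The same section gives the censoring rule: "A patient without any MAHE will be censored at the end of the last cycle (i.e. last cycle of placebo or trilaciclib), death". Two further dates, the study end and the last contact, also censor, and the earliest of the four applies. Only two statuses result, event and censored.

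SAP 6.2.7.2.1 says that the endpoint, overall and for each component, "will be summarized similar to DSN, Strategy 2 as described in" SAP 6.2.7.1.5. There, the DSN Strategy 2 "endpoint will be summarized using Kaplan-Meier method", with median and quartiles, a stratified p-value, and a hazard ratio "calculated from a Cox proportional hazard model in which treatment and the stratification factors will be included as fixed effects". A plot is promised in both places: "For the time (days) to first occurrence of a MAHE event, a graphical display of cumulative incidence will be presented" in 6.2.7.1.5, and "A graphical display of cumulative incidence will also be presented" in 6.2.7.2.1. Neither says how the plotted incidence is estimated, and neither document names a competing-risk method.

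SAP 5.1.3.1 counts a MAHE only between randomization and the end of the last induction cycle. In this SAP, MAHE is a supportive secondary endpoint, and its main analysis is a negative binomial model for the number of events.

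**The concern.** Kaplan-Meier treats a censored patient as someone who could still have the event and is represented by those still at risk. That does not describe a patient who has died. One minus Kaplan-Meier with death censored estimates the risk in a population where nobody dies. A plot labelled cumulative incidence will be read as the share of patients who had a MAHE by each time, and with the statuses in 5.1.3.1 it would sit above that share.

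What is at stake is the absolute level of the curves and the quartiles, overall and for each component. In a disease with appreciable early mortality, the report could show a median time to first MAHE although fewer than half the patients had one.

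The SAP does not leave death as plain censoring elsewhere. In the first sensitivity analysis for binary endpoints (6.2.7.1.5), a patient who dies in induction without an event is assigned a definite outcome. The time-to-first analysis has no matching rule.

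**Working it through.** The documents state no MAHE proportion, event count or power for this analysis, so there is no figure to reproduce. The check has three parts: direction, size, and the plausible range of early mortality.

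**Direction.** Let H1(t) be the cumulative hazard of a first MAHE and H2(t) that of death without a prior MAHE.

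- Kaplan-Meier with death censored: 1 − KM(t) = ∫ exp(−H1) dH1.
- Cumulative incidence: F(t) = ∫ exp(−H1 − H2) dH1.

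The second integrand is never larger than the first, so F(t) ≤ 1 − KM(t). The inequality is strict once a death precedes a later MAHE. This needs no assumption about rates.

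**Size.** Inputs:

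- Window: about 14 weeks. Three 21-day cycles plus Day 36 of the fourth (SAP section 5, end of cycle where no maintenance follows) is 63 + 36 = 99 days.
- Net MAHE risk over the window (risk if nobody died): 55% placebo, 35% trilaciclib. Assumed.
- Net risk of death without a prior MAHE over the window: 8% or 22%. Assumed.
- Constant hazards, with a = −ln(1 − net MAHE risk) and b = −ln(1 − net death risk).

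Then 1 − KM equals the net MAHE risk, and F = [a/(a + b)] × [1 − exp(−a − b)].

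For 55% and 22%: a = 0.7985, b = 0.2485, a/(a + b) = 0.7627, and 1 − 0.45 × 0.78 = 0.649. So F = 0.7627 × 0.649 = 49.5%.

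| Net MAHE risk (1 − KM) | Net death risk | True cumulative incidence | Excess |
|---|---|---|---|
| 55% | 8% | 53.1% | 1.9 points |
| 55% | 22% | 49.5% | 5.5 points |
| 35% | 8% | 33.7% | 1.3 points |
| 35% | 22% | 31.3% | 3.7 points |

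The death risks are net figures. In the 55% rows the share actually dying before a first MAHE is 58.6 − 53.1 = 5.5% and 64.9 − 49.5 = 15.4%.

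*Comparison of arms.* The ratio is 55/35 = 1.57 by 1 − KM, against 53.1/33.7 = 1.58 at 8% and 49.5/31.3 = 1.58 at 22%. The difference goes from 20.0 points to 19.4 and 18.2.

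*Median (55% row).* Kaplan-Meier puts it at 14 × ln 2 / 0.7985 = 12.2 weeks. The cumulative incidence reaches 50% at 12.8 weeks with 8% deaths. With 22% it has not reached 50% by week 14.

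*Precision.* With about 53 patients per arm (106 in total), the standard error of a proportion near 50% is √(0.25/53) = 6.9 points, so each excess above is less than one standard error.

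**Plausible early mortality.** Protocol 4.1 gives a median survival of 8 to 10 months and 2-year survival below 10%.

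- Exponential survival at those medians gives 24% to 20% dead by 3.22 months (14 weeks). It also implies 12.5% to 19% alive at 2 years, which contradicts the second figure.
- A Weibull curve through the median and 10% at 2 years gives 23% (median 8) to 14% (median 10).
- With 5% at 2 years it gives 19% to 10%.

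So 22% sits at the top of the range. Two features pull it down: entry requires a predicted life expectancy of at least 3 months, and only deaths before a first MAHE count.

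**The case against.** The strongest reply is that little depends on this. It is a sensitivity analysis of a supportive endpoint, outside the five-hypothesis procedure. The planned Kaplan-Meier outputs are quartiles, a p-value and a hazard ratio. Event-free rates at fixed times are specified for OS and PFS, not here, and no absolute difference between arms is planned. The proportion with an RBC transfusion on or after week 5 is analysed directly as a key secondary endpoint. All-cause hospitalization is itself a component, so many deaths may follow a MAHE and do no harm. All of this stands, and it is why the point is minor.

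A second reply is that the plot's estimator is not named, so one minus Kaplan-Meier is an inference. That is true as text. But 5.1.3.1 defines only event and censored, and a cumulative-incidence function run on that variable equals one minus Kaplan-Meier. Naming an estimator would not help unless death gets its own status.

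A reader might go further and infer that censoring at an early end of induction is the same error. The documents do not support that. For binary endpoints, the tipping-point analysis in 6.2.7.1.5 treats event-free patients with fewer than four induction cycles as missing, not as known non-events. The models in 6.2.7.1.1 and 6.2.7.2.1 use offsets for cycles or weeks of induction. Censoring at the end of exposure is the time-to-event counterpart of that approach. Whether early stopping should compete is a choice of target, although the SAP does not state its target here.

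**Conclusion.** The point holds for death. The censoring rule, the Kaplan-Meier summary and the cumulative-incidence display are all in the SAP, and the direction of the error is certain. Its size cannot be fixed from the documents. Under constant hazards and an assumed 55% net MAHE risk, the excess is about 2 points at 8% net deaths and about 5.5 points at 22%, a likely upper bound. A higher MAHE risk would raise it somewhat; deaths that follow a hospitalization would shrink it.

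A reader might infer that the treatment effect on MAHE is overstated. That is not supported: in the illustration the arm ratio stays at about 1.57 to 1.58, and the Cox hazard ratio remains valid as a cause-specific quantity. If deaths before a first MAHE differed by arm, the distortion of the absolute curves would differ too, but nothing in the documents points to that. The negative binomial count analysis and the multiplicity-controlled tests are untouched. The protocol makes MAHE a key secondary endpoint for Region 1, but through event counts, and that region's SAP is not among the documents.

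**What to change.** In SAP 5.1.3.1, give death before a first MAHE its own status as a competing event.

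In 6.2.7.2.1, and where 6.2.7.1.5 mentions the MAHE plot:

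- Use the Aalen-Johansen estimator by arm for the cumulative-incidence display and the quartiles, overall and for each component.
- Report the crude proportion of patients with at least one MAHE alongside.
- Label the Cox hazard ratio as cause-specific.

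Early end of induction may stay censored, with one sentence stating the target, for example the risk if patients stayed on induction. The crude proportion will then still differ from the curve for patients who stop early, and that sentence will explain why. A version that treats early end as competing is optional.

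The cost is a few lines of SAP text and a standard software option. No new data are needed. The only downside is that the reported incidence becomes slightly lower.
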